6.3.9.2 Regulatory Reporting of SAEs

Following notification from the site PI or appropriate sub-investigator, DMID, as the IND sponsor, will report any SUSAR in an IND safety report to the FDA and will notify all participating site PIs as soon as possible. DMID will report to the FDA any unexpected fatal or life-threatening suspected adverse reaction as soon as possible, but in no case later than 7 calendar days after the sponsor's initial receipt of the information. If the event is not fatal or life-threatening, the IND safety report will be submitted within 15 calendar days after the sponsor determines that the information qualifies for reporting as specified in 21 CFR Part 312.32. Relevant follow up information to an IND safety report will be submitted as soon as the information is available. Upon request from FDA, DMID will submit to the FDA any additional data or information that the agency deems necessary, as soon as possible, but in no case later than 15 calendar days after receiving the request. SAEs that are not SUSARs will be reported to the FDA at least annually in a summary format which includes all SAEs. Sites may have additional local reporting requirements (to the IRB and/or national regulatory authority).

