1.1.6 Other Data

CONFIDENTIAL

This material is the property of the Applied Biology Inc. Do not disclose or use except as authorized.

The PI has not identified any additional data related to the safety or efficacy of this study.

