6.3.2 Definition of Serious Adverse Event (SAE)

An SAE is defined as “An AE or suspected adverse reaction is considered serious if, in the view of either the investigator or the sponsor, it results in any of the following outcomes: Death, a life-threatening AE, inpatient hospitalization or prolongation of existing hospitalization, a persistent or significant incapacity or substantial disruption of the ability to conduct normal life functions, or a congenital anomaly/birth defect. Important medical events that may not result in death, be life-threatening, or require hospitalization may be considered serious when, based upon appropriate medical judgment, they may jeopardize the patient or subject and may require medical or surgical intervention to prevent one of the outcomes listed in this definition. Examples of such medical events include allergic bronchospasm requiring intensive treatment in an emergency room or at home, blood dyscrasias or convulsions that do not result in inpatient hospitalization, or the development of drug dependency or drug abuse.” “Life-threatening” refers to an AE that at occurrence represents an immediate risk of death to a subject. An event that may cause death if it occurs in a more severe form is not considered life-threatening. Similarly, a hospital admission for an elective procedure is not considered a SAE. All SAEs, as with any AE, will be assessed for severity and relationship to study intervention. All SAEs will be recorded on the appropriate SAE CRF. All SAEs will be followed through resolution or stabilization by a licensed study physician (for IND studies, a physician listed on the Form FDA 1572 as the site PI or Sub-Investigator). All SAEs will be reviewed and evaluated by DMID and will be sent to the SMC (for periodic review), and the IRB/IEC.

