6.3.9 Serious Adverse Event Reporting

6.3.9.1 Investigators Reporting of SAEs

Any AE that meets a protocol-defined criterion as a SAE must be submitted immediately (within 24 hours of site awareness) on an SAE form to the DMID Pharmacovigilance Group, at the following address:

DMID Pharmacovigilance Group
Clinical Research Operations and Management Support (CROMS)
[name]
[name]
SAE Hot Line: [name] (US) or [name] (outside US) SAE FAX
Number: [name] (US) or [name] (outside US) SAE Email Address:
[contact]

Other supporting documentation of the event may be requested by the DMID Pharmacovigilance Group and should be provided as soon as possible. The DMID Medical Monitor will review and assess the SAE for regulatory reporting and potential impact on study subject safety and protocol conduct. At any time after completion of the study, if the site PI or appropriate sub-investigator becomes aware of an SAE, the site PI or appropriate sub-investigator will report the event to the DMID Pharmacovigilance Group.

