The study monitor will keep a separate record at the monitor's office of each subject's identification number, the treatment administered to the subject (arm assignment), outcomes and any laboratory results.

No other data will be recorded. No personal information will be kept outside the study site.

Data compiled at the end of the study will not include any information that can be used to identify individuals.

The site will keep all subject records for a minimum of 3 years after the completion of the study.

12 Finance and Insurance

The Principal Investigator will be responsible for the cost of study. The site carries insurance for accidental injury. There is no other insurance.

APPENDIX 1

Drugs that should be used cautiously with Proxalutamide

Strong CYP3A4 inducer
Avamibe, Carbamazepine, Phenytoin, Rifampicin, Mitotan, Nevirapine, Phenobarbital, Rifabutin, Rifapentine, St. John's wort, Alfentanil, Ryclosporin, Dihydroergotamine / Ergotamine, Fentanyl, Irinotecan, Pimozit, Quinidine, Sirolimus, Tacrolimus
Moderate CYP3A4 inducer
Smacet, Tavern, Bosentan, Efaviron, Etruverin, Lopinavir, Modafinil, Nafceillin, Thalidazine, Tiranavir, Ritonavir
Strong CYP3A4 inhibitor
Posidovir, Clarithromycin, Conivatan, Indinavir, Itraconazole, Ketoconazole, lopinavir / Ritonavir, Mibedil, Nefazodone, Nefenavir, Posaconazole, Ritonavir, Saquinavir, Trapivir, Taliomycin, Voriconazole, Etigavir / Ritonavir, Fluconazole, Tiranavir / Ritonavir, Acetamycin
Moderate CYP3A4 inhibitors
Apronavir, Aripitan, Azanavir, Casopitam, Cimetidine, Ciprofloxacin, Clazotinib, Cyclosporin, Dalunavir, Diltiazem, Dronedarone, Erythromycin, Imatinib, Tofesoyang, Verapamil
Sensitive CYP3A4 substrates
Remifentanil, Aripiptam, Budesonide, Buspirone, Conivatan, Daphnesin, Darunavir, Dasatinib, Dronedarone, Eletroptan, Eplerenone, Everolimus, Felodipine, Indinavir, Fluticasone, Lopinavir, Lovastatin, Lulasidone, Maravelo, Midazolam, Nisoldipine, Quetiapine, Saquinavir, Sildenafil, Simvastatin, Sirolimus, Tolvaptan, Tiranavir, Triazolam, Vardenafil
Narrow therapeutic index CYP3A4 Substrate
Astemizole, Cisapride, Cyclosporine, Dihydroergotamine, Fentanyl, Pethidine, Quinidine, Tacrolimus, Terfenadine
Sensitive CYP2D6 substrates
Tomoxetine, Decipamine, Dextromethorphan, Metoprolol, Nebeprolol, Perphenazine, Tolterodine, Venlafaxine, Avamibe, Carbamazepine, Phenytoin sodium, Rifampicin

Narrow therapeutic index CYP2D6 Substrate

Thioridazine

Revision History				

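### Section 6 rests central SAE assessment, regulatory reporting and committee review on DMID and an SMC, and routes unanticipated problems to an SDCC, but the rest of the visible protocol connects none of them to this trial

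*Combined protocol and SAP*

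**What the plan says.** All references are to the current protocol version, which includes the female cohort.

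- **Site reporting (6.3.9.1).** An SAE "must be submitted immediately (within 24 hours of site awareness) on an SAE form to the DMID Pharmacovigilance Group". The same section adds that "The DMID Medical Monitor will review and assess the SAE for regulatory reporting" and for its possible effect on subject safety. SAEs that a site learns of after the study has ended take the same route.
- **Evaluation (6.3.2).** "All SAEs will be reviewed and evaluated by DMID and will be sent to the SMC" for periodic review, and also to the IRB/IEC.
- **Regulatory reporting (6.3.9.2).** "DMID, as the IND sponsor, will report any SUSAR in an IND safety report to the FDA", and it "will notify all participating site PIs as soon as possible". For unexpected fatal or life-threatening reactions the limit is "in no case later than 7 calendar days after the sponsor's initial receipt of the information". Other SUSARs have a 15-day limit.
- **Unanticipated problems (6.4.2).** These go to the IRB and to a recipient written as the SDCC, a slash, and the study sponsor. The limit is 24 hours if the problem is an SAE and 3 days otherwise.

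Elsewhere, the page footer states: "This material is the property of the Applied Biology Inc". Section 12 states: "The Principal Investigator will be responsible for the cost of study".

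**The concern.** A safety reporting rule works only if its recipient is part of the trial. Here the rule is explicit about where reports go, so this is more than missing detail. Followed literally, it places four functions on bodies with no visible link to the trial: central assessment of each SAE, reporting to the FDA, warning the other sites, and periodic committee review.

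The regulatory clock is affected as well. The 7-day limit runs from the sponsor's receipt of the information. If the text leaves unclear who the sponsor is, it also leaves unclear when the clock starts.

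The most serious events take this route. Death is an SAE under 6.3.2, and the proportion of deaths is a secondary outcome in 3.1.

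**Working it through.** No arithmetic applies, and the plan has no figure to reproduce. The check was to trace each body through the current protocol and the final statistical plan, and then to ask which functions remain without it.

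**Step 1. Where each body appears.**

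| Body | Sections that mention it | Sections outside section 6 |
|---|---|---|
| DMID | 6.3.2, 6.3.9.1, 6.3.9.2 | none |
| SMC | 6.3.2 | none |
| SDCC | 6.4.2 | none |

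No visible text gives their membership, charter or relation to this trial.

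**Step 2. What the sections that should connect to them say.**

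| Section | Who is named |
|---|---|
| 3.3 Randomization and blinding | none of the three |
| 7.4 Interim analysis (efficacy and safety at 50% recruitment) | no reviewing body |
| 7.5 Termination (includes a treatment-caused SAE) | no deciding body |
| 7.6 Analysis | a biostatistics expert and an outside consultant |
| 9 Quality control | a study monitor, who audits procedures and CRFs |
| 11 Records | the study monitor, who holds arm assignment, outcomes and laboratory results |
| 12 Finance | the PI, who bears the cost |
| Ownership notice | a private company |

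The visible part of the abbreviation list includes SAE, AE, ARDS and UP but none of the three bodies. This is weak support, because the start of the list may be on a removed page.

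**Step 3. What remains if DMID, the SMC and the SDCC are set aside.**

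| Function | Still assigned to someone else? |
|---|---|
| Judging seriousness, severity and causality | Yes: on-site investigator (6.3.4), PI or designee (6.3.6) |
| Recording the SAE and following it to resolution | Yes: SAE CRF and a licensed study physician (6.3.2) |
| Informing ethics committees | Yes: IRB/IEC for SAEs (6.3.2), IRB for unanticipated problems (6.4.2) |
| Informing a sponsor of unanticipated problems | Yes, but the sponsor is not identified (6.4.2) |
| Central assessment of each SAE | No: DMID only |
| IND safety reports to the FDA | No: DMID only |
| Warning other sites of a SUSAR | No: DMID only |
| Periodic committee review of SAEs | No: SMC only |

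**Step 4. Consistency within section 6.** The sponsor is DMID in 6.3.9.2, is paired with the SDCC in 6.4.2, and is unnamed in 6.3.11 on pregnancy. For unanticipated problems that are SAEs, 6.4.2 refers back to the SAE reporting process, which leads to DMID again.

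**The case against.** **The route is not empty.** This stands. A reader might infer that nobody reviews accumulating harm. The documents do not support that: the IRB/IEC receives all SAEs, a study physician follows them up, an interim look at safety data is planned, and a monitor audits the CRFs. The gap is limited to the four functions marked as unassigned above.

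**Section 7.5 does not need DMID to recognise a treatment-caused SAE.** This also stands. Causality is judged on site under 6.3.4 and 6.3.6. That 7.5 names no decision-maker is a separate matter.

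**The SDCC does not receive every SAE.** Correct. Under 6.4.2 it receives unanticipated problems, including those that are SAEs, and the study sponsor is named beside it.

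**DMID may be the sponsor.** A reader might infer from the footer and the cost clause that it is not. An ownership notice and a payment clause do not designate an IND sponsor, title and signature pages are removed, and section 10 does refer to the IND regulations. The documents settle the question neither way. Nor do they show that the text was carried over from another protocol. The point needs neither inference, since it rests on the absence of any link between section 6 and the rest of the plan.

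**The earlier version's safety section names none of these bodies.** That text is superseded and the revision log records an amended AE section, so the difference is not evidence of error and is not used here.

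**It is too late to redirect reports.** Partly right. The final statistical plan was written during manuscript preparation, so an edit cannot change where past reports went. But 6.3.9.1 keeps the route open after the study ends, and the route actually used can still be stated.

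**Conclusion.** The concern holds as an unreconciled reporting chain and should be corrected. Section 6 makes DMID the central assessor, the regulatory reporter and the source of warnings to other sites, and makes an SMC the periodic reviewer. It sends unanticipated problems to an SDCC or study sponsor. No other visible section gives these bodies a role, and the sections that describe how the trial is run name different people.

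The rule covers every SAE. The documents give no expected SAE rate for this trial, so no count of affected reports is offered. No sample size, power, type I error or effect estimate depends on the point.

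The conclusion assumes that the removed title and signature pages do not themselves set out roles for DMID, an SMC and an SDCC. If they do, what remains is to carry those roles into the body of the protocol. The documents do not show that any report failed to arrive.

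**What to change.** Reconcile 6.3.2, 6.3.9.1, 6.3.9.2 and 6.4.2 with sections 7, 9, 11 and 12, in one of two ways:

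- **If DMID, the SMC and the SDCC are not part of this trial,** replace them with the trial's actual sponsor role, safety contact, regulatory reporter and the body that reviews SAEs.
- **If DMID does hold the IND,** say so in the oversight sections, and define the SMC and SDCC there and in the interim analysis and termination sections (7.4 and 7.5).

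In either case, use one designation for the sponsor throughout, so that it is clear whose receipt starts the reporting clock. State which route was used for SAEs already reported. This point asks for no change to the stated time limits.

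The cost is text edits in four safety sections, matching entries in the oversight sections, and a short statement of the route used. No new patients, outcome data or analyses are needed.

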6.3.10 Reporting Events to Subjects

Subjects will be informed of any severe AEs or SAEs that occur as part of their participation in this trial.

6.3.11 Reporting of Pregnancy

Pregnancy is not defined as an AE. However, any pregnancy that occurs during study participation should be reported to the sponsor on the appropriate CRF. Pregnancy should be followed to outcome.

6.4 *Unanticipated Problems*

6.4.1 Definition of Unanticipated Problems (UP)

An Unanticipated Problem is any event, incident, experience, or outcome that meets the following criteria:

- Unexpected in terms of nature, severity, or frequency given (a) the research procedures that are described in the protocol-related documents, such as the IRB-approved research protocol and informed consent document; and (b) the characteristics of the subject population being studied;
- Related or possibly related to participation in the research ("possibly related" means there is a reasonable possibility that the incident, experience, or outcome may have been caused by the procedures involved in the research); and
- Suggests that the research places subjects or others at a greater risk of harm (including physical, psychological, economic, or social harm) than was previously known or recognized.

6.4.2 Unanticipated Problem Reporting

To satisfy the requirement for prompt reporting, unanticipated problems (UP) will be reported using the following timeline: UPs that are SAEs will be reported to the IRB and to the Statistical and Data Coordinating Center (SDCC)/study sponsor within 24 hours of the investigator becoming aware of the event per the above describe SAE reporting process. Any other UP will be reported to the IRB and to the SDCC/study sponsor within 3 days of the investigator becoming aware of the problem.

6.4.3 Reporting Unanticipated Problems to Subjects

Subjects will be informed of any UPs that occur as part of their participation in this trial.

7 Statistical Plan

7.1 *Statistical Methods*

I. General Principles:

- Double-blinded, placebo controlled randomized interventional study with a two-sided type I error rate of 0.05.
- Continuous variables will be expressed as median (interquartile range [IQR]) and categorical variables will be expressed as a number
- 95% confidence intervals will be calculated for the primary outcome
- Group comparisons will be analyzed by the Wilcoxon rank sum test or χ^2 test
- The placebo arm will be used as a reference group when calculating treatment effects
- Differences between rates of clinical improvement will be calculated using unadjusted ordinal logistic regression or Cox proportional hazard models
- Statistical analyses will be conducted using XLSTAT version 2020.5.1 (Addinsoft, Inc.)

II. Statistical Hypotheses:

The primary endpoint is the distribution of clinical assessments on the COVID-19 ordinal scale at day 14. The primary outcome will be analyzed using the Wilcoxon rank sum test.

The Null Hypothesis (H_0) is that the distribution of clinical assessments on the COVID-19 ordinal scale at day 14 among hospitalized COVID-19 subjects treated with Proxalutamide is equal to the distribution of clinical assessments on the COVID-19 ordinal scale at day 14 among hospitalized COVID-19 subjects treated with the Proxalutamide placebo

The Alternative Hypothesis (H_A) is that the distribution of clinical assessments on the COVID-19 ordinal scale at day 14 among hospitalized COVID-19 subjects treated with Proxalutamide is not equal to the distribution of clinical assessments on the COVID-19 ordinal scale at day 14 among hospitalized COVID-19 subjects treated with the Proxalutamide placebo

Mathematically written as:

$$H_0: P(X > Y) = P(Y > X)$$

$$H_A: P(X > Y) \neq P(Y > X)$$

Where X and Y are randomly selected clinical assessments from the two treatment arms in the study.

III. Primary Efficacy Analysis:

- The non-parametric Wilcoxon rank sum test (Mann Whitney U) will be used to assess the primary end point.
- P-values <0.05 will be considered significant. All statistical analysis will be based on the intent-to-treat (ITT) population. All missing data will be described.

7.2 Sample Size Estimates

Assumptions:

- The sample size estimation is based on the results reported in the placebo arm of the Adaptive COVID-19 Treatment Trial (NCT04280705)
- On day 15, 61% of subjects in NCT04280705 placebo group remained hospitalized.
- The odds ratio of improvement in the ordinal scale in the Proxalutamide arm compared to the Proxalutamide placebo is at least 2.0
- The study has two arms with randomization at 1:1 ratio
- 90% power to detect an odds ratio of 2.0 using a two-tailed test with a type I error rate of 5%
- According to NCT04280705 protocol “The sample size to detect a given odds ratio for 1:1 randomization using a 2-tailed test at level α is estimated by the equation below. λ is the log odds ratio, p_i is the overall probability (combined over both arms) of being in the i th category of the K ordinal outcomes, and $z_{\alpha/2}$ and z_{β} are the $1 - \alpha/2$ and $1 - \beta$ quantiles of the standard normal distribution.”

$$\frac{12(z_{\alpha/2} + z_{\beta})^2}{\lambda^2(1 - \sum_{i=1}^K p_i^3)}$$

- The estimated distribution is based on NCT04280705 protocol scenario 4
- 3.5% of the subjects will not complete the study based on NCT04280705

Sample Size Estimate:

CONFIDENTIAL

This material is the property of the Applied Biology Inc. Do not disclose or use except as authorized.

Based on the assumptions above, we calculated that at a minimum we would need to recruit for each cohort 294 subjects (147 subjects in each arm) i.e., a total of approximately 600 subjects.

7.3 Subject Population(s) for Analysis

- The primary analysis will be based on the intent-to-treat (ITT) population. The data from all subjects enrolled in the study will be analyzed.
- The safety analysis will be based on a modified intent-to-treat (MITT) population i.e., subjects who received at least one dosage of the interventional treatment.
- Subgroup analysis based on: 1) age stratification; and 2) androgen status as defined by the “Gabrin sign” or “PCOS signs” will be conducted for the primary and secondary outcomes.

7.4 Interim Analysis

Interim efficacy and safety data will be made upon recruitment of 50% of the subjects.

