3.3 Randomization

During the enrollment phase (admission to hospital), each subject will be assigned a subject study number. The first subject will be assigned the number 001 and each subject thereafter will be assigned a consecutive number i.e., 002, 003, etc.

In each cohort, subjects will be randomized into 1 of 2 arms in a 1:1 ratio each receiving an interventional treatment.

Arm 1: Subjects administered Proxalutamide 300mg q.d for 14 days + standard of care as determined by the PI at the site

Arm 2: Subjects administered Proxalutamide placebo 300mg q.d for 14 days + standard of care as determined by the PI at the site

In each cohort, each subject will be randomized using an interactive web software: Randomizer.at. The blinding table layout will be a single block. The randomization method used will be permuted blocks of size 4.

This is a blinded study. Neither participants, nor investigators, nor the study team will be aware of treatment assignments prior to the final data base locks at the conclusion of the study (or the interim analysis).

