7.5 Termination Criteria

Upon occurrence of any one of the events listed below, the study will terminate or be modified accordingly:

- Completion of the study by a sufficient number of subjects (294 subjects) to reach our confidence level
- Termination of Arm 1: Serious adverse event due to treatment with Proxalutamide
- Substantial evidence of treatment difference between the arms. The study design will be modified to an open-label study.

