Differences between rates of clinical improvement will be calculated using unadjusted ordinal logistic regression or Cox proportional hazard models	We used Kaplan-Meier's survivor function for estimates of proportion surviving, and failure function for estimates of alive hospital discharges. Cox proportional hazards model was kept only to calculate hazard ratio (HR) for death and its 95% confidence interval (CI). Graphical assessment and Kaplan-Meier versus predicted survival showed that of the proportional-hazards assumption has not been violated	For better demonstration of the 95% CI and timeline of the evolution of the outcomes in figures. For measure of effect, as stated in the Primary and Secondary outcomes, we adopted relative risk (or Risk Ratio) for easier understanding.
Statistical analyses will be conducted using XLSTAT version 2020.5.1 (Addinsoft, Inc.)	Statistical analysis was conducted using Stata/SE version 16.1 for Mac (StataCorp LLC, College Station, TX, USA).	Preference of the team performing statistical analysis

4. Statistical hypothesis

As proposed in the final protocol	Done in the final statistical Plan	Rationale

The primary endpoint is the distribution of clinical assessments on the COVID-19 ordinal scale at day 14. The primary outcome will be analyzed using the Wilcoxon rank sum test.
	
The primary efficacy endpoint was described as the overall 14-day recovery ratio. This effect measure was obtained after dichotomization of the COVID-19 ordinal scale for scores 2 and 1, representing patients that were discharged from hospital.
	
Although the distribution is still presented graphically, and tested for statistical significance, a clear cut-off point in the COVID-19 ordinal scale was used to obtain the Overall Recovery Ratio. Recovery ratio is a clinically meaningful effect measure.

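### The efficacy interim has no defined 50%, no significance level and an open-label trigger without a criterion, so the plan secures neither its 5% type I error nor blinded outcomes after the look

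*Combined protocol and SAP*

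**What the plan says.** References are to the current protocol (the version with male and female cohorts) unless stated otherwise.

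- **7.4 Interim Analysis**, in full: "Interim efficacy and safety data will be made upon recruitment of 50% of the subjects". No test, endpoint, level, analyst or committee is named.
- **7.5 Termination Criteria** lists events on which "the study will terminate or be modified accordingly". One of them reads: "Substantial evidence of treatment difference between the arms. The study design will be modified to an open-label study".
- **7.1 Statistical Methods** sets a "two-sided type I error rate of 0.05" and one decision rule: "P-values <0.05 will be considered significant". It makes no allowance for an interim look.
- **7.2 Sample Size Estimates** plans to "recruit for each cohort 294 subjects (147 subjects in each arm) i.e., a total of approximately 600 subjects".
- **3.3 Randomization** says participants, investigators and the study team will not know assignments "prior to the final data base locks at the conclusion of the study (or the interim analysis", with the interim named in parentheses as an alternative to the final lock.
- **3.2 Study Design/Type** has the PI assess each subject daily for the study outcomes.
- **6.3.2** names a safety committee, for periodic review of serious adverse events only.
- **The final statistical plan** keeps a 5% type I error (its section 6) and makes the 14-day recovery ratio, scores 1 and 2, the primary effect measure. On the ordinal distribution it adds: "Although the distribution is still presented graphically, and tested for statistical significance". It states that its changes were made while the manuscript was being written. It does not mention the interim.

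**The concern.** A comparative efficacy look with a consequence attached needs three things fixed in advance: when it happens, what result triggers action, and who sees it. Here all three are open.

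The first stake is the type I error. If a result at the look can support a claim, the trial-wide error depends on a level that the plan never gives, and a final p<0.05 cannot be read at face value.

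The second is blinding. The only action named for a treatment difference is to open the label. From then on the PI who scores patients daily could know the arm. Discharge, which defines recovery and so the primary effect measure, is partly a decision of the treating team and therefore open to influence.

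**Working it through.** **1. What 50% could mean.** Section 7.2 gives two denominators:
- whole trial: 0.5 × 600 = 300 (or 0.5 × 588 = 294, taking 2 × 294);
- per cohort: 0.5 × 294 = 147.

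Section 7.4 chooses neither. Section 7.5 also lists 294 completers as an end point without saying whether this is per cohort or in total.

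**2. Recruited is not the same as evaluable.** The trigger is recruitment, but the primary endpoint is at Day 14, so the most recent recruits have no outcome at the look. Assume that 80–100% of those enrolled have Day-14 data (my range; the documents give none).
- Information fraction, whole-trial reading: 0.8 × 300 / 600 = 0.40, up to 300 / 600 = 0.50.
- Patients without a Day-14 outcome at the look, whole trial: 600 − 300 = 300, up to 600 − 0.8 × 300 = 360.
- The same per cohort: 294 − 147 = 147, up to 294 − 0.8 × 147 ≈ 176.

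These are the patients whose Day-14 assessment an open-label switch could reach.

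**3. Type I error.** The plan's 5% is exact for one test at 0.05. With one interim look it is reproduced only if the look supports no claim. Otherwise, for a single primary test, let Z1 and Z2 be the interim and final statistics, bivariate normal with correlation √t, where t is the information fraction. Under the null hypothesis the error is P(|Z1| > c1 or |Z2| > c2), with c2 = 1.960 (final p<0.05).

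| Level at which the look may support a claim | c1 | Error, t = 0.5 | Error, t = 0.40 |
|---|---|---|---|
| no claim possible | – | 5.00% | 5.00% |
| 0.001 | 3.291 | 5.02% | 5.04% |
| 0.01 | 2.576 | 5.5% | 5.6% |
| 0.05 | 1.960 | 8.3% | 8.6% |

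The documents do not select a row.

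**4. Matched pairs that hold 5%.** Solving the same expression for 0.0500 at t = 0.5, with power at drift 1.960 + 1.282 = 3.242 (a design with exactly 90.0% power for one test at 0.05):

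| Boundary | Interim / final two-sided level | Power |
|---|---|---|
| O'Brien-Fleming | 0.0052 / 0.0480 | 89.8% |
| Lan-DeMets, O'Brien-Fleming type | 0.00305 / 0.0490 | 89.9% |
| 0.001 at the look | 0.001 / 0.0498 | 90.0% |

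The Lan-DeMets pair moves with the information: at t = 0.40 it is 0.0008 / 0.0497. A level set for 50% recruited would therefore be wrong for the data actually in hand.

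**5. Blinding, passages side by side.** Section 3.3 can mean that the blind ends at the interim, or that nobody is unblinded before the lock for whichever analysis is run. Section 7.5 needs no such interpretation: if its condition is met, the design becomes open-label. Section 3.2 then leaves the PI scoring the remaining patients. Section 7.6 provides for a statistician and an outside verifier, but no passage restricts who sees interim results by arm.

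**The case against.** **No passage lets the interim reject the null hypothesis.** The opening line of 7.5 allows termination or modification, but the item on a treatment difference names only conversion to open-label. If the look supports no claim, repeated testing adds no error. This stands. A reader might infer that the trial's type I error is 8.3%; the documents do not support that, because it needs a claim at p<0.05 at the look, which the plan neither grants nor rules out. The silence is the defect.

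**The open-label switch depends on an interim difference.** With no true effect it would be uncommon. A reader might want a false-positive rate for the lost blind, but any such rate would need blinding to be lost whatever the look showed, plus an invented size of bias. Only one of two readings of 3.3 would support the first assumption. I attach no figure.

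**The cohorts.** Because 7.2 sizes men and women separately, a reader might infer two primary tests and add a multiplicity penalty. Section 7.1 states one hypothesis for all subjects, and the final statistical plan has one overall recovery ratio, with sex as a subgroup without hypothesis tests. The primary test is best read as pooled.

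**Other unblinding material.** The change of randomization at a remote hospital (final statistical plan, section 2) and the monitor's record of arm assignments (protocol section 11) might be taken as evidence that the interim broke the blind. Neither is linked to the interim.

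**Timing.** The final statistical plan is a retrospective table of changes. Its silence shows neither that the look was run nor that it was dropped. That limits the remedy but leaves the gap.

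**Conclusion.** The concern holds. As written, the plan does not secure its stated 5%. For one pooled primary test with the final at 0.05 and t = 0.5, the error lies between 5% (no claim at the look) and 8.3% (claim allowed at 0.05, an illustrative worst case), with 5.02% and 5.5% for levels of 0.001 and 0.01. If only 80% of recruits have Day-14 data the upper figure is 8.6%. These values are conditional on the look being able to support a claim.

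Separately, a switch under 7.5 would leave the remaining patients' discharge and scores to be assessed unblinded. On the whole-trial reading that is about 300 to 360 of 600, under the assumed 80–100% availability. Those data would be open to bias of unknown size. The documents do not show that the look took place, that 7.5 was triggered or that anyone was unblinded.

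**What to change.** 1. In 7.4, define the 50% as a stated number of patients with Day-14 data in the single pooled primary test. Name that test, since the final statistical plan tests both the recovery ratio and the ordinal distribution.
2. State one matched two-sided pair for it, for example Lan-DeMets O'Brien-Fleming-type 0.00305 / 0.0490 at t = 0.5, recomputed for the actual information fraction. Alternatively, state that the interim supports no efficacy claim and no efficacy-driven design change.
3. In 7.5, replace the undefined evidence criterion and the open-label switch with that boundary, and keep randomised patients and assessors blinded through Day 28.
4. Restrict unblinded interim results to a person or group independent of the sites and study team. If the safety committee in 6.3.2 is used, write that remit. Remove the parenthetical reference to the interim in 3.3, or limit it to that group.
5. In the final statistical plan, disclose whether the look took place, on how many patients, at what level, who saw it, and whether 7.5 was triggered.

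**Cost.** Items 1–4 are mainly wording, plus an independent person or group for the look. For one primary test designed at 90.0% power, power becomes about 89.8–90.0%, with no change in sample size. These items protect only a look that has not yet happened; if it has, item 5 is all that remains.
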